# PROTOCOL AMENDMENT SUMMARY OF CHANGES TABLE

DOCUMENT HISTORY		
Document	Date	DNG Number
Amendment 4	10-Jul-2018	2016N290015_04
Amendment 3	01-Dec-2017	2016N290015_03
Amendment 2	07-Nov-2017	2016N290015_02
Amendment 1	03-May-2017	2016N290015_01
Original Protocol	04-Apr-2017	2016N290015_00

Amendment 4 10-JUL-2018

# **Overall Rationale for the Amendment:**

This is a substantial amendment with changes to the inclusion and exclusion criteria to more accurately reflect the patient population.

Section # and Name	Description of Change	Brief Rationale					
14dillo	*Bolded text indicates newly added text, and strikethrough indicates deleted text.						
6.1 Inclusion Criteria #3	The following change was made:  Idiopathic pulmonary arterial hypertension (IPAH), hereditary pulmonary arterial hypertension (HPAH), or PAH associated with collagen vascular disease, repaired congenital heart disease, or appetite suppressant use.	PAH associated with repaired congenital heart disease was removed as this differs clinically from other forms of PAH.					
6.1 Inclusion Criteria #5	The following change was made:  Hemodynamically stable on background therapy with no evidence of uncontrolled right heart failure (historic data), as determined by the investigator.	This change clarifies that participants with uncontrolled right heart failure must be excluded. However, participants with controlled right heart failure can be included as determined by the investigator.					
6.1 Inclusion Criteria #6 and 9.4 Six-minute walk test	The following change was made:  Six minute walk (6MW) distance, as performed at screening or within 6 months prior to screening, of ≥100 meters and ≤ 450 ≤ 500 meters.	Six-minute walk maximum distance was increased to 500 meters to allow participants to be included that meet all other criteria.					
6.1 Inclusion Criteria #10	The following change was made:  Body weight <90 ≤ 100 kg and body mass index (BMI) within the range 18-30 35 kg/m² (inclusive).	Maximum BMI was increased to 35 to more accurately reflect the range observed in the patient population.					
6.2 Exclusion criteria #4	The following change was made:  Complex repaired and unrepaired congenital heart disease.	This change clarifies that both complex repaired and unrepaired congenital heart disease will be excluded from the study.					
6.2 Exclusion criteria #9	The following change was made:  Estimated glomerular-filtration-rate (eGFR)  < 60 45 mL/min/1.73m².	eGFR rate was reduced to 45ml/min/1.73m² to more accurately reflect the range observed in the patient population.					
12.2 Appendix 2: Clinical Laboratory Tests	The following change was made: Activated Prothrombin time (PT) a PTT	Q2 confirmed the assay they use is activated prothrombin time (aPTT)					

## CONFIDENTIAL

Section # and Name  12.2 Appendix 2: Clinical Laboratory Tests	*Bolded text indicates newly added text, and strikethrough indicates deleted text.  The following change was made:  Local laboratory results are only required in the event that the central laboratory results are not available in time for either study treatment administration and/or response evaluation. If a local sample is required, it is important that the sample for central analysis is obtained at the same time. Additionally, if the local laboratory results are used to make either a study treatment decision or response evaluation, the results must be entered into the CRF.	This change allows sites to use local labs, if necessary; however, it ensures samples are always collected and analysed centrally.
12.5 Appendix 5: Contraceptive Guidance and Collection of Pregnancy Information	Pregnancy testing, with a high sensitivity test will be performed using the test kit provided by the central laboratory /and approved by the sponsor and in accordance with instructions provided in its package insert.	This change gives flexibility for sites to use local labs for pregnancy testing.

## 1. SYNOPSIS

**Protocol Title:** An Open-label, Dose-escalation Study to Evaluate the Safety, Tolerability, Pharmacokinetics and Pharmacodynamics of Single Doses of GSK2586881 in Participants with Pulmonary Arterial Hypertension

**Short Title:** Study to Evaluate the Safety, Pharmacokinetics and Pharmacodynamics of GSK2586881 in Participants with Pulmonary Arterial Hypertension

## Rationale:

GSK2586881 is a purified intravenous (IV) formulation of soluble recombinant human Angiotensin Converting Enzyme (rhACE2) that is being investigated as a potential treatment for Pulmonary Arterial Hypertension (PAH).

Angiotensin converting enzyme type 2 (ACE2) is a type I, membrane-bound carboxypeptidase that inactivates Angiotensin II (Ang II) by cleaving it to produce Ang(1-7). Ang II is a key effector peptide of the Renin-Angiotensin-System (RAS) that can exert deleterious effects on the pulmonary vasculature resulting in vasoconstriction, proliferation and inflammation, all of which contribute to PAH development. Conversely Ang(1-7) has shown vasodilatory, anti-proliferative and anti-inflammatory properties by signalling through the Mas receptor and recombinant ACE2 has proven effective in blocking or treating established PAH in several rodent models.

ACE2 hydrolyses a number of other biological peptides, including converting Ang I to Ang(1-9) and removing the C-terminal residue from the bradykinin metabolites [des- $Arg^9$ ]-bradykinin and lys[des- $Arg^9$ ]-bradykinin .

GSK2586881 has been tested in healthy subjects and mechanically ventilated patients with Acute Respiratory Distress Syndrome (ARDS) and has been shown to be well tolerated with the rapid modulation of RAS peptides. This will be the first GlaxoSmithKline (GSK) study to test the safety and preliminary effects on pulmonary hemodynamics of GSK2586881 in participants with PAH.

A detailed description of the biology, pharmacology, efficacy, and safety of GSK2586881 is provided in the Investigator's Brochure (IB).

# **Objectives and Endpoints:**

Objectives	Endpoints							
Primary								
To evaluate changes in the pulmonary hemodynamics after single IV doses of GSK2586881 administered to participants with PAH receiving background PAH therapy.	Change from baseline in pulmonary vascular resistance (PVR), cardiac output (CO) and mean pulmonary artery pressure (mPAP), as data permit							

	Objectives	Endpoints							
Sec	condary								
•	To evaluate the safety and tolerability of single IV doses of GSK2586881 administered to participants with PAH receiving background PAH therapy.	•	Adverse events (AE), clinical laboratory values, vital signs, electrocardiogram (ECG), pulse oximetry and immunogenicity.						
•	To evaluate the effect of single IV doses of GSK2586881 on RAS peptide responses in participants with PAH receiving background PAH therapy.	•	Change from baseline of pulmonary wedge and systemic RAS peptides (e.g. Ang II, Ang(1-7), Ang(1-5), and AngII/Ang(1-7) ratio).						
•	To evaluate the effect on biomarkers of disease activity after single IV doses of GSK2586881 administered to participants with PAH receiving background PAH therapy.	•	Change from baseline in NT pro-BNP, NO and cardiac troponin I.						
•	To evaluate the pharmacokinetics (PK) of GSK2586881 after single IV doses of GSK2586881 in participants with PAH receiving background PAH therapy.	•	Plasma concentrations of GSK2586881 and derived PK parameters.						

# **Overall Design:**

This is a Phase IIa, open-label, dose-escalation, single dose study in participants with PAH (as defined in the eligibility criteria) whose symptoms have been clinically stable for 8 weeks prior to enrolment and who have had no change in PAH-specific therapy in the 12 weeks prior to enrolment.

#### **Number of Participants:**

The total number of participants recruited will be determined through an ongoing review of the safety, tolerability, PK and PD data with a minimum of 4 participants recruited per cohort. There will be 4 cohorts. At the end of each cohort a dose escalation meeting will occur and a decision will be made whether to dose escalate.

A maximum of 27 participants will complete dosing and critical assessments in this study.

If participants prematurely discontinue the study, additional replacement participants may be recruited and assigned to the same dose level at the discretion of the Sponsor in consultation with the investigator.

#### **Treatment Groups and Duration:**

The study will comprise of 4 separate cohorts. Participants will be administered a single dose at the following planned doses: 0.1, 0.2, 0.4, or 0.8mg/kg.

[figure not shown]
Dose escalation will occur after a minimum of 4 participants have been dosed per cohort and review of safety, tolerability, PK and hemodynamic data up to 24h post dose has taken place. Dose escalation will continue up to a maximum dose of 0.8mg/kg.

Cohort sizes may vary with a minimum of 4 participants per cohort. Additional participants may be enrolled to expand a dosing cohort to further evaluate findings at a given dose level.

It is anticipated that the total duration of participation in the study will be up to a maximum of 59 days from screening to the last study visit.

### Study Design

# Single Dose (minimum 4 participants per cohort)

\* dose escalation meeting (review of safety, PK and hemodynamic data)

# 2. SCHEDULE OF ACTIVITIES (SOA)

Procedure	Screening (up to 28				Trea	ntment Pe	riod				Follow- up Day 7- 14	Follow- up Day 28 ± 3 days	Notes
	days before dosing)	Pre- dose 	0h	0.08h (5 min) 	0.5h	1h	2h	4h	8h	24h		,	
Informed consent	Х												
Genetics consent	Х												Genetics consent is Optional
Inclusion and exclusion criteria	X												Recheck clinical status before randomization and/or 1st dose of study medication
Demography	Х												
Full physical examination including height and weight	Х												
Medical history (includes substance usage and family history of premature CV disease)	х												Substances: drugs, alcohol, tobacco and caffeine
Past and current medical conditions	Х												

	Screening				Trea	atment Pe	riod				Follow- up	Follow- up Day	Notes
Procedure	(up to 28					Day 7- 14	28 ± 3 days						
	days before dosing)	Pre- dose 	0h	0.08h (5 min) 	0.5h	1h	2h	4h	8h	24h		,	
Serum OR urine pregnancy test (WOCBP only)	Х	X									X		
FSH and estradiol test (postmenopausal females only as needed)	Х												
Human Immunodeficiency Virus (HIV), Hepatitis B and C screening	Х												If test performed within 3 months prior to first dose of study treatment, testing at screening is not required
Functional classification	X												
6 Minute Walk Distance	X3												
Admission		Х											Participants may be admitted the day before dosing to enable completion of required pre-dose time point assessments.
Brief physical		Х									Х		
Study Treatment			Х										

Procedure	Screening (up to 28				Trea	Follow- up Day 7- 14	Follow- up Day 28 ± 3 days	Notes					
	days before dosing)	Pre- dose 	0h	0.08h (5 min) 	0.5h	1h	2h	4h	8h	24h		auyo	
Vital Signs	X	X			X	X	X	X	X	X	v		Vital signs will be measured after 5 minutes supine at all time points.
Vitai Signs	^	۸			۸	۸	^	۸	۸	^	X		Triplicate blood pressure (BP) will be taken at screening only.
Pulse Oximetry (SpO 2 )	Х	X			X	Х	Х	X	X	Х	Х		Pulse oximetry will be measured and recorded with each blood pressure assessment
Laboratory assessments (include liver chemistries, haematology panel and coagulation panel)	Х	X								Х	Х		
Urinalysis	Х									Х			
12-lead ECG	Х	Х						X		Х	х		Triplicate will be performed at Screening and Predose

Procedure	Screening (up to 28				Trea	Follow- up Day 7- 14	Follow- up Day 28 ± 3 days	Notes					
Frocedure	days before dosing)	Pre- dose 	0h	0.08h (5 min) 	0.5h	1h	2h	4h	8h	24h		uays	
Telemetry			←						→				Monitoring to start 30min prior to treatment administration and continue throughout the study until 24h after dosing
Right heart catheter Insertion		←						<del>)</del>					RHC inserted prior to dose and removed after the 4h hemodynamic measurement
Blood sample for biomarkers of disease activity		Х					Х	Х		Х			
Blood sample for Nitric Oxide		Х					Х	Х		Х			
Blood sample for PK		Х		Х	Х	Х	Х	Χ	Х	Х			
Blood sample for immunogenicity		X									Х	Х	Additional visits may be required. (see Section 9.7 for details).

Procedure	Screening (up to 28				Trea	ntment Pe	riod				Follow- up Day 7- 14	Follow- up Day 28 ± 3 days	Notes
	days before dosing)	Pre- dose 	0h	0.08h (5 min) 	0.5h	1h	2h	4h	8h	24h		auyo	
Blood sample for renin- angiotensin system biomarkers		X		х	Х	Х	X	х	X	х	х		
Blood sample for pulmonary wedge RAS biomarkers		Х				Х	Х	Х					
Hemodynamic measurements		Х				Х	х	х					
Genetic sample		Х											Can be taken any time after consent has been signed. Only required once and is optional.
Discharge										Х			
AE review		←==	======			==>	Х						
SAE review	Х	←==	←										
Concomitant medication review 	Х	Х									Х		

Pre-dose measurements may be taken any time after admission up until dosing.
 Procedures will be completed immediately after dosing has completed.

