### 4. OBJECTIVES AND ENDPOINTS

Objectives	Endpoints
Primary	
To evaluate changes in the pulmonary hemodynamics after single IV doses of GSK2586881 administered to participants with PAH receiving background PAH therapy.	Change from baseline in pulmonary vascular resistance (PVR), cardiac output (CO) and mean pulmonary artery pressure (mPAP), as data permit
Secondary	
To evaluate the safety and tolerability of single IV doses of GSK2586881 administered to participants with PAH receiving background PAH therapy.	Adverse events (AE), clinical laboratory values, vital signs, ECG, pulse oximetry and immunogenicity.
To evaluate the effect of single IV doses of GSK2586881 on RAS peptide responses in participants with PAH receiving background PAH therapy.	
 
Change from baseline of pulmonary wedge and systemic RAS peptides (e.g. Ang II, Ang(1-7), Ang(1-5), and AngII/Ang (1-7) ratio).
 

Objectives	Endpoints
To evaluate the effect on biomarkers of disease activity after single IV doses of GSK2586881 administered to participants with PAH receiving background PAH therapy.	Change from baseline in NT pro-BNP, NO and cardiac troponin I.
To evaluate the pharmacokinetics of GSK2586881 after single IV doses of GSK2586881 in participants with PAH receiving background PAH therapy.	Plasma concentrations of GSK2586881 and derived PK parameters.
Exploratory	
To evaluate PK/PD relationships after single IV doses of GSK2586881.	Pulmonary wedge RAS peptides, and/or pulmonary vascular hemodynamic measurements compared with PK exposure.
To evaluate pharmacogenetics(PGx).	Evaluate I/D polymorphisms in the Angiotensin Converting Enzyme (ACE) gene and analyze the impact on Ang II (and possibly other RAS peptides), and responses to GSK2586881 administration.

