# 5.2. Number of Participants

The total number of participants recruited will be determined through an ongoing review of the safety, tolerability, PK and PD data with a minimum of 4 participants recruited per cohort. There will be 4 cohorts. At the end of each cohort a dose escalation meeting will occur and a decision will be made whether to dose escalate.

Once dose escalation is complete additional participants may be recruited to further evaluate findings at a given dose level. A maximum of 27 participants will complete dosing and critical assessments in this study.

Evaluable participants are defined in Section 10.2.

If participants prematurely discontinue the study, additional replacement participants may be recruited and assigned to the same dose level at the discretion of the Sponsor in consultation with the investigator.

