# 5.4. Scientific Rationale for Study Design

The lack of a placebo arm is justified in that the primary goals of this study are to understand the initial hemodynamic effects, safety and tolerability of GSK2586881 in a small number of participants with PAH.

Due to the open label design it is accepted that there may be potential bias in AE reporting, this will be taken into account when interpreting the study results.

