#### 9.6. Pharmacokinetics

Whole blood samples will be collected for measurement of plasma concentrations of GSK2586881 as specified in the SoA (Section 2). The actual date and time (24-hour clock time) of each sample will be recorded.

Additional sample time points may be added during the study if warranted and agreed upon between the investigator and the sponsor, however, the maximum allowed blood volume will not be exceeded.

Samples collected for analyses of GSK2586881 plasma concentration may also be used to evaluate safety or efficacy aspects related to concerns arising during or after the study.

Once the plasma has been analyzed for GSK2586881 any remaining plasma may be analyzed for other compound-related metabolites and the results reported under a separate protocol.

Details of blood sample collection (including volume to be collected), processing, storage and shipping procedures are provided in the lab manual.

Plasma analysis will be performed under the control of GSK, the details of which will be included in the lab manual.

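### Footnote 1 of the Schedule of Activities lets the only scheduled baseline blood sample for systemic RAS peptides, NO, NT-proBNP and troponin I be drawn the day before dosing for some participants and just before the dose for others

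*Protocol*

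**What the plan says.** The Schedule of Activities (protocol Section 2) has one pre-dose column. Its footnote 1 reads: "Pre-dose measurements may be taken any time after admission up until dosing". The note on the Admission row reads: "Participants may be admitted the day before dosing to enable completion of required pre-dose time point assessments".

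In the same table, systemic RAS peptides, nitric oxide and the disease-activity biomarkers (NT-proBNP and troponin I, as Section 9.8 defines them) each have one scheduled pre-dose sample and none at screening. After the dose, systemic RAS peptides are sampled from 5 minutes to 24 hours and again at Day 7-14. The other three are sampled at 2, 4 and 24 hours only.

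Section 4 defines the secondary endpoints as "Change from baseline of pulmonary wedge and systemic RAS peptides" and "Change from baseline in NT pro-BNP, NO and cardiac troponin I". Section 5.4 confirms the absence of a control: "The lack of a placebo arm is justified".

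Section 9.6 says of the PK samples: "The actual date and time (24-hour clock time) of each sample will be recorded". Section 9.8, on biomarkers, has no such sentence. It refers to the Schedule of Activities for what is collected and to the lab manual, which is not at hand, for the details of collection and handling.

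**The concern.** A change from baseline can be read as a drug response only if the baseline stands for the participant's state at dosing. Here the baseline may have been taken under other conditions: on another day, at another time of day, and possibly before the catheter went in, whereas the systemic samples at 1, 2 and 4 hours are drawn with it in place. The caffeine restriction in Section 6.3.1 counts back 2 hours from dosing, so it need not cover a sample drawn the day before.

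With no concurrent control, a systematic non-drug difference between the early sample and the moment of dosing cannot be told apart from a drug effect in the mean change. With mixed timing, participants in one cohort also have baselines that mean different things.

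The baseline carries some weight in the rationale. Section 5.5 predicts that from 0.2 mg/kg upwards Ang II stays, on average, below the participant's own baseline for at least 24 hours. Section 10.3.1 plans plots of RAS peptides against PVR, CO and mPAP, and the baselines of the two sides could come from different days.

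**Working it through.** **Does the text permit it?** Footnote 1 sets the earliest pre-dose time at admission, and the Admission note allows admission on the previous day for the very purpose of completing pre-dose assessments. Nothing in the protocol narrows this for the biomarker samples, and Section 9.8 points back to the schedule. Early sampling is therefore permitted, but not required. With a single scheduled pre-dose sample, an analysis rule such as taking the last value before dosing would select that same sample.

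**What is exposed?** Systemic RAS peptides, NO, NT-proBNP and troponin I. The hemodynamic measurements and the pulmonary wedge RAS samples need the catheter in place and are not part of this point.

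**Form of the bias.** The protocol states no figure to reproduce; Section 10.1 says the sample size has no statistical basis. Let d be the mean non-drug difference between an early sample and one taken just before dosing, in units of the SD of the change. Let f be the fraction of a cohort sampled early.

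- Bias in the cohort mean change = f × d.
- Standard error of the mean change = 1/√n, in the same units.
- Bias in standard errors = f × d × √n.

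**Inputs.** n = 4 is the minimum cohort (Sections 5.2 and 7.2). Section 5.2 adds: "A maximum of 27 participants will complete dosing and critical assessments in this study". If all four cohorts run and three stay at the minimum, the largest single cohort is 27 − 3 × 4 = 15. The values of d and f are assumptions.

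| Assumed d (SD) | n = 4, f = 1 | n = 4, f = 0.5 | n = 15, f = 1 | n = 15, f = 0.5 |
|---|---|---|---|---|
| 0.1 | 0.20 | 0.10 | 0.39 | 0.19 |
| 0.25 | 0.50 | 0.25 | 0.97 | 0.48 |
| 0.5 | 1.00 | 0.50 | 1.94 | 0.97 |

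(√4 = 2; √15 = 3.873.) For each d, the f = 1 columns are upper bounds. For a given f, the bias does not shrink when a cohort is expanded; only the standard error does.

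**Added variance from mixed timing.** If each participant is sampled early with probability f, the shift adds f(1 − f)d² to the variance of the change. At f = 0.5 and d = 0.5 this is 0.25 × 0.25 = 0.0625, so the SD rises by the factor √1.0625 = 1.03. The shift alone thus costs little precision. A weaker correlation between an older baseline and the later values could cost more. With SD(change) = SD × √(2(1 − ρ)), an assumed fall in ρ from 0.9 to 0.6 raises SD(change) from 0.45 to 0.89 SD. With 4 participants, the standard error then rises from 0.22 to 0.45 SD.

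**The case against.** The case on the other side is substantial.

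- **A permission is not a practice.** Sites may draw nearly all samples just before the dose. A reader might infer that the shift enters every cohort's mean in full. The documents do not support that: it would need every participant sampled early, and footnote 1 only allows it.
- **The shift is not in the documents.** Participants must be on stable background therapy (Section 6.1), so d may be small. The table shows what assumed values would do and is not evidence of an actual bias.
- **Some of it can be checked.** A reader might infer that the problem is beyond any remedy once samples are taken. For systemic RAS peptides that goes too far. The Day 7-14 sample is plausibly free of drug, given that Section 9.3 uses at least 3 days as the monitoring period until drug is undetectable after an overdose. It offers a partial check. NO, NT-proBNP and troponin I have no such later sample.
- **Dose comparisons suffer less.** An offset common to all cohorts cancels between doses. The planned regressions use PVR, CO and mPAP, which are not affected here.
- **A same-day sample is not perfect either.** One taken just before dosing does not match the clock time of the 2, 4 and 8 hour samples, and within-day variation remains.
- **The lab manual may narrow the window or require times to be recorded.** That cannot be excluded. Silence in Section 9.8 does not show that sampling times go unrecorded. Still, Section 9.8 says samples are collected as the schedule specifies, and the schedule expressly permits early sampling.

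The telemetry note ("Monitoring to start 30min prior to treatment administration") could be read as an inconsistency with footnote 1. It is not: it governs monitoring and sets no baseline window.

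What stands is that the protocol fixes a wide window where a narrow one would serve these endpoints better.

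**Conclusion.** The point holds as a minor design weakness. The protocol allows the only scheduled baseline for four groups of change-from-baseline endpoints to be taken at uneven distances from dosing, in an uncontrolled study with cohorts as small as 4. The resulting bias is f × d, with both quantities unknown. Under assumed shifts of 0.1 to 0.5 SD it is at most 0.2 to 1.0 standard errors with 4 participants, and at most 0.39 to 1.94 with 15, if everyone is sampled early; it is proportionally less otherwise. NO, NT-proBNP and troponin I are the more exposed, since systemic RAS peptides have the Day 7-14 sample as a partial check.

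The consequence is limited. These endpoints are secondary and their analysis is descriptive (Section 10.3.1). The escalation review in Section 7.2 names safety, tolerability, PK and hemodynamic data. Section 10.3.3 lets the remaining pharmacodynamic data inform further recruitment at a dose level, but sets no threshold on these analytes. A reader might extend the point to the primary hemodynamic endpoints; the need for the catheter to be in place keeps them outside it.

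**What to change.** Amend footnote 1 so that the baseline blood samples for systemic RAS peptides, NO, NT-proBNP and troponin I are taken on the day of dosing, within one short window before the dose that is stated in the protocol and common to all participants. Add to Section 9.8 that the actual date and time of these samples are recorded, as Section 9.6 already provides for PK, and that it is noted whether the baseline sample was drawn before or after catheter insertion. Keep the present freedom for the other pre-dose items, such as the brief physical examination and the safety laboratory, immunogenicity and genetic samples.

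The cost is less scheduling freedom for sites on the day of dosing. No visit, procedure or blood draw is added. The change brings the baseline closer to dosing conditions and makes it comparable across participants. It does not remove within-day variation, which should be acknowledged when the changes are interpreted.
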